2 ABSTRACT

Title: A post-authorisation, non-interventional, retrospective, drug-utilisation study to describe the pattern of use of lenalidomide in patients with myelodysplastic syndromes (MDS)

Rationale and Background: Revlimid[®] (lenalidomide) is a drug belonging to the proprietary series of drugs with immunomodulatory and other properties, and is currently registered in several countries worldwide, including the European Union (EU), for the treatment of multiple myeloma in combination with dexamethasone in adult patients who had received at least one previous therapy, for the treatment of adult patients with previously untreated multiple myeloma (MM) who are not eligible for transplant, and for the treatment of adult patients with

Confidential and Proprietary

relapsed or refractory mantle cell lymphoma. Lenalidomide also is licensed in more than 20 countries including the United States (US), Australia, Japan, New Zealand, Israel, and Switzerland for the treatment of transfusion-dependent anaemia due to International Prognostic Scoring System (IPSS) low- or intermediate-1 (int-1)-risk MDS with deletion 5q (del(5q)), with or without additional cytogenetic abnormalities. In the EU, the Committee for Medicinal Products for Human Use (CHMP) adopted a positive Opinion on 25-Apr- 2013 for the use of Revlimid in the "treatment of transfusion-dependent anaemia due to low- or int-1-risk MDS associated with an isolated deletion 5q cytogenetic abnormality when other therapeutic options are insufficient or inadequate," variation EMEA/H/C/717/II/056. The European Commission (EC) Decision was adopted on 13-Jun-2013 based on a condition to the EU marketing authorisation for the Marketing Authorisation Holder (MAH) to implement a non-interventional post-authorisation safety study (PASS) (Revlimid, Annex IID to the EC Decision). As per the condition to the marketing authorisation, the MAH implemented this retrospective drug-utilisation study to describe the post-marketing pattern of use of lenalidomide in MDS both within and outside of the EU approved indication.

This lenalidomide retrospective study will also aim to gather additional safety information among MDS patients treated with lenalidomide outside the EU approved indication including the risk of progression to acute myeloid leukemia (AML) in a routine-care setting.

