The main secondary objective of the study is to assess incidence and time to progression to AML in off-label patients. Assuming a proportion of around 50%, at least 230 patients in the study will be off-label. Assuming the proportion of patients progressing to AML will be similar to those on-label, ie, 17%, 230 off-label patients will yield a 95% CI = (12.3%, 22.4%).

Incidence and time to progression to AML in on-label patients will be assessed as well for reference. Kaplan-Meier curves and hazard-ratios between on- and off-label patients will be derived and adjusted in multivariate analyses for confounding and risk factors. This will be requested to each registry, and the sponsor will provide all registries with the same statistical guidance to perform those specific analyses.

Data Analysis:

The following analyses will be performed according to the availability of data from the data sources.

For all variables

• Descriptive statistics (mean, standard deviation, median, interquartile range, minimum, and maximum) will be provided for continuous variables; categorical variables will be summarised using frequency and percentages.

Demographic data and baseline characteristics

• Demographic data and baseline characteristics will be described including age, time from diagnosis to treatment, RBC transfusion burden, complete blood counts (CBCs) (white blood cells [WBC], platelets, hemoglobin levels), ferritin level, relevant medical history, co-morbidities, previous treatment of MDS and response to previous treatments, current co-medications, morphology and cytogenetic results (MDS subtype, blast count, karyotype), and data on risk classifications (IPSS).

Study drug exposure

The primary objective of the study is to describe the pattern of use of lenalidomide in the clinical routine practice of MDS patients. The proportion of patients receiving lenalidomide outside of the EU approved indication will be provided and will be associated with its 2-sided 95% CI. For lenalidomide, indication for which lenalidomide is used and dosing including any adjustments will be summarised using descriptive statistics. Duration of dosing will be similarly summarised together with a summary of dosing interruptions. Duration of exposure and cumulative dose of lenalidomide will also be described. Data on the use of relevant concomitant medication will also be reported.

Safety analysis

Safety analyses will be based on both the on- and off-label cohorts.

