In the seminal Phase 2, uncontrolled study (MDS-003) conducted in patients with low- or int-1–risk MDS del(5q) and transfusion dependence (median of 6 red blood cell [RBC] transfusions in the 8 weeks preceding study entry), patients were treated with lenalidomide at the

initial dose of 10 mg/day for 21 days (46 patients) or 28 days (102 patients) of each 28-day cycle (List, 2006). Seventy-six percent of 148 patients included in the study had a significant improvement of transfusion dependence and 67% of patients became transfusion independent. The median time to response to lenalidomide was rapid (4.6 weeks) and sustained; the median duration of transfusion independence was not achieved at the time of the primary publication, after a median follow-up of 104 weeks. The median increase in hemoglobin levels compared to baseline values was 5.4 g/dL. Thrombocytopenia and an increased transfusion need at study inclusion were predictive factors of no response.

Eighty-five patients were evaluable for the cytogenetic response (at least 20 cells in metaphase available both at study entry and after 24 weeks); of them 45% had a complete cytogenetic response, and 28% a partial cytogenetic response (decrease \geq 50% of the initial del(5q) clone size) (List, 2006).

A recent randomized, placebo-controlled, double-blind, Phase 3 study (MDS-004) compared 2 different initial regimens of lenalidomide (respectively 10 mg/day for 21/28 days and 5 mg/day continuously, in 28-day cycles) with placebo (Fenaux, 2011). After 16 weeks of double-blind treatment, patients who did not have at least a minor erythroid response (50% or greater reduction in transfusion numbers, compared to baseline) could interrupt the double-blind phase and continue the treatment with active drug in an open-label phase. The vast majority of patients initially allocated to placebo (except for 11 patients) crossed over to the active drug after 16 weeks. For all patients, the double-blind phase was interrupted after 52 weeks, and the study continued as open-label for up to 156 weeks (3 years). The primary endpoint was the transfusion independence maintained for at least 26 weeks (according to the International Working Group [IWG] criteria [Cheson, 2006]), and secondary endpoints were rate of erythroid response, cytogenetic response, overall survival (OS), rate of progression to AML, safety, and Health--related Quality of Life (HRQoL).

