An interim descriptive report was prepared 1 year after study start. Within the interim descriptive report, available data on eligible patients regarding the pattern of use of lenalidomide within and outside the EU approved indication, namely the distribution of MDS patients according to predefined categories (eg, transfusion-dependent IPSS low- or int-1-risk MDS with isolated del(5q), or with additional cytogenetic abnormalities, or IPSS risk categories int-2 or high, or patients with MDS without del(5q)) was presented. On 29-Mar-2019, the first interim descriptive report was submitted to the Pharmacovigilance Risk Assessment Committee (PRAC) in order to discuss if the data collected on lenalidomide use, across different groups of MDS patients, are sufficient to allow successful completion of this study. The Assessment Report adopted by the CHMP on 27-Jun-2019 included a request to submit another interim descriptive report in Quarter (Q)1 2020. On 27-Mar-2020, the second interim descriptive report was submitted to PRAC (EMEA/H/C/000717/ANX/041.8). The final Assessment Report, adopted by the CHMP on 10-Dec-2020, concluded that the post-authorisation measure for the second interim report was fulfilled with no further action required.

The final data analysis will occur after at least 460 patients have been included and will be based on data from all eligible patients available at that time.

Data will be collected for both on- and off-label patients, to cover the period from date of first lenalidomide dose (baseline) until the date of death or last follow-up available at the time of the retrospective data collection (whichever occurs first) including for patients lost to follow-up or who discontinue the drug for any reason. Data collected at baseline will include those data that could have been generated earlier but are relevant at the baseline date (for example, information related to diagnosis).

Time to progression to AML or time to any other kind of event will be counted from the date of first lenalidomide dose (baseline).

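### Plain means and medians of duration of dosing understate time on lenalidomide to the extent that patients are still on drug at last follow-up, and the protocol does not label them as observed exposure

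*Protocol*

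**What the plan says.** - **Protocol, Abstract, Data Analysis, Study drug exposure.** The paragraph opens with the primary objective, pattern of use, and plans descriptive statistics for dosing. It then says: "Duration of dosing will be similarly summarised together with a summary of dosing interruptions", and: "Duration of exposure and cumulative dose of lenalidomide will also be described". It defines neither duration of dosing nor duration of exposure.
- **Abstract, For all variables.** "Descriptive statistics (mean, standard deviation, median, interquartile range, minimum, and maximum) will be provided for continuous variables". Section 7.7 repeats the list without the interquartile range.
- **Section 7.1.1.** Data run from first dose "until the date of death or last follow-up available at the time of the retrospective data collection", and the final analysis "will be based on data from all eligible patients available at that time". The selection criteria in 7.1.2 set no minimum follow-up.
- **Kaplan-Meier.** Sections 7.6 and 7.7.3 request it from each registry for progression to AML only.
- **Section 7.7.2.** The main-text section on use patterns contains no analysis of duration of dosing.
- **Table 4.** The lenalidomide entries are indication, starting dose, adjustments and interruptions. No stop date or on-treatment status is named.

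**The concern.** Time on drug is right-censored for anyone still treated when observation stops. A plain mean or median takes the time seen so far as the whole duration, so the error can only be downward. For equal follow-up it grows with the true duration. Cumulative dose carries the same error.

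The protocol uses a censoring-aware method for AML in the same patients but plans none for time on drug. How long patients stay on lenalidomide is part of the pattern of use that the study is meant to describe, and an unlabelled median will be read as the answer to that question.

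**Working it through.** The protocol gives no figure for duration or for the share still on drug, so there is none to reproduce. The check asks how far a plain summary falls below the truth under stated assumptions.

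**Inputs from the protocol**
- Earliest EU start: "The European Commission (EC) Decision was adopted on 13-Jun-2013".
- Estimated end of data collection: Q2 2023 (Table 2). The longest follow-up is therefore about 120 months.
- Second interim report, submitted 27-Mar-2020 (section 7.5): 212 + 149 + 11 = 372 patients. Against the target of 460 this is 372/460 = 80.9%, about 39 months before the end of Q2 2023.

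**Assumptions**
- Time on drug T is exponential with true median m, so S(t) = 2^(−t/m).
- Potential follow-up C is independent of T, there is no loss to follow-up, and the final total is near 460.

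**Formulas.** Let G(t) be the share of patients with potential follow-up beyond t.
- The observed time is min(T, C), so the plain median solves S(t)·G(t) = 0.5.
- The plain mean is the integral of S(t)·G(t).
- The share still on drug is 1 − (ln 2/m) × plain mean.

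**Two start patterns**
- Front-loaded, from the interim count: 80.9% of patients have follow-up spread evenly over 39 to 120 months, and 88/460 = 19.1% over 0 to 39 months. For t below 39, G(t) = 1 − 0.1913·t/39.
- Even starts over 10 years: G(t) = 1 − t/120.

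**Worked line, m = 24**
- Front-loaded, t = 20.36: S = 2^(−20.36/24) = 0.5555; G = 1 − 0.1913 × 20.36/39 = 0.9001; product 0.500.
- Even, t = 18.28: S = 2^(−18.28/24) = 0.590; G = 1 − 18.28/120 = 0.848; product 0.500.

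| True median (months) | Front-loaded: still on drug | Plain median | Shortfall | Even: still on drug | Plain median | Shortfall |
|---|---|---|---|---|---|---|
| 6 | 4% | 5.75 | 4% | 7% | 5.6 | 7% |
| 12 | 9% | 11.0 | 8% | 14% | 10.4 | 13% |
| 24 | 22% | 20.4 | 15% | 28% | 18.3 | 24% |

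Means behave alike. At m = 24 the true mean is 24/ln 2 = 34.6 months, and the plain mean is 27.1 (front-loaded) or 24.9 (even).

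**Two further checks**, by simulation of 1,000,000 patients with even starts:
- The Kaplan-Meier median, censoring those still on drug, returns 6.0, 12.0 and 24.0.
- Adding an assumed 10% yearly loss to follow-up lowers the plain medians to 5.2, 9.3 and 15.0.

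**The case against.** **Observed exposure is a legitimate quantity.** The protocol never says that the summary estimates time to discontinuation, and plain statistics correctly describe exposure accrued to last follow-up. This stands, and it is why labelling is the first part of the fix. The protocol does not say that this is what it means, however.

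**The detail may be left to the SAP.** Section 7.7 calls itself an overview, and the SAP is not at hand and may settle the matter. This stands in part: the estimator itself is already named in the protocol, and an SAP that follows the text inherits it.

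**Even starts overstate the effect.** They would place 81/120 = 67.5% of patients by March 2020, against 80.9% on the interim count. The summary of changes also reports a low rate of new patients and an earlier eligibility date. This stands, so the front-loaded figures are the better guide, although loss to follow-up would push the other way.

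**Stronger readings that a reader might infer**
- *Many patients are still on drug.* No section gives the share.
- *The on-label cohort is hit hardest.* No section says which cohort is treated longer, and the ordering also needs similar follow-up. Section 5.2 does report for the phase 2 study that "the median duration of transfusion independence was not achieved at the time of the primary publication". That is duration of response in a trial, not time on drug in routine care, and it is silent on off-label patients.
- *An on-/off-label difference in duration is biased.* No such contrast is planned.
- *The primary result is biased.* The study is sized on the off-label proportion, which censoring of treatment time does not touch. Duration is primary only under the broad pattern-of-use wording.

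**Conclusion.** The point holds conditionally. Unlabelled means and medians of duration understate time on lenalidomide to the extent that patients are still treated at last follow-up, and for equal follow-up they do so more when the true duration is longer.

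For true medians of 6 to 24 months, the shortfall in the plain median is about 4% to 15% with front-loaded starts and 7% to 24% with even starts. Both ranges assume exponential time on drug and no loss to follow-up. If treatment is short and follow-up long, the effect is minor. The true share still on drug is unknown from the protocol.

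This is a cheap improvement to a descriptive output and does not threaten the sized result.

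**What to change.** 1. In the Abstract (Study drug exposure), label the plain summaries of duration of exposure and cumulative dose as *observed to last follow-up*, and report the number still on drug per cohort. Add the same text to 7.7.2, which has no duration analysis to amend.
2. Add a Kaplan-Meier estimate of time to permanent discontinuation for any reason including death, censoring patients still on drug at last follow-up. Each registry would produce it by cohort, alongside its AML Kaplan-Meier analysis. Section 7.9 rules out pooling raw data, so give a pooled estimate only where the pseudonymised datasets allow it.
3. Add lenalidomide stop date, or on-treatment status at last follow-up, to Table 4, as far as available.

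Cost: wording, one additional variable and one additional output per registry. The variable should be requested before the final data transfer. Where a registry cannot supply it, only the labelled observed exposure can be reported for that source.

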3 AMENDMENTS AND UPDATES

The following four updates to the original protocol were generated following input from the Pharmacovigilance Risk Assessment Committee (PRAC):

- Protocol Amendment No. 1 (Version 5.0) dated 26-Oct-2017
- Protocol Amendment No. 1 (Version 4.0) dated 07-Jul- 2017
- Protocol Amendment No. 1 (Version 3.0) dated 14-Dec-2016
- Protocol Amendment No. 2 (Version 1.0) dated 31-May-2021
- Protocol Amendment No. 3 (Version 1.0) dated 21-Jul-2022

This protocol Amendment No. 3 (Version 2.0) – dated 10-Aug-2022 describes changes to the proposed sample size in light of a lower availability of patient data in the registries than expected, with minimal impact on the range of the confidence intervals. In addition, the date of eligibility

for patient data was changed from the date of reimbursement to the date of EU-approval for the MDS indication in the interest of further patient numbers. A clarification on the exclusion criteria was also included. Planned dates for milestones were adjusted for data collection and all dependent milestones to ensure that the final data transfer would not be collected before this amendment was approved.

4 MILESTONES

Milestones for this study are summarised in Table 2.

Milestone	Planned Date
Start of data collection ^a	Q1 2018 ^a
First interim descriptive report	29-Mar-2019 (date of submission to PRAC, EMEA/H/C/000717/ANX/041.7)
Second interim descriptive report	27-Mar-2020 (date of submission to PRAC, EMEA/H/C/000717/ANX/041.8)
Estimated end of data collection	Q2 2023 (to be confirmed once registries have updated their databases)
Study progress report(s)	
PSUR	As per PSUR cycle
Other study progress reports	On request from PRAC/NCAs
Final report of study results	Q2 2024

Table 2:Milestones

EMEA = European Medicines Agency; NCA = National Competent Authority; PRAC = Pharmacovigilance Risk Assessment Committee; PSUR = Periodic Safety Update Report; Q1 = first quarter; Q4 = fourth quarter.

^a Refers to study start

5 RATIONALE AND BACKGROUND

5.1 Rationale

Revlimid (lenalidomide) is a drug belonging to the proprietary series of drugs with immunomodulatory and other properties, and is currently registered in several countries worldwide, including the EU, for the treatment of multiple myeloma in combination with dexamethasone in adult patients who had received at least one previous therapy, for the treatment of adult patients with previously untreated MM who are not eligible for transplant, and for the treatment of adult patients with relapsed or refractory mantle cell lymphoma. Lenalidomide also is licensed in more than 20 countries including the United States (US), Australia, Japan, New Zealand, Israel, and Switzerland for the treatment of transfusion-dependent anaemia due to International Prognostic Scoring System (IPSS) low- or intermediate-1 (int-1)-risk MDS with deletion 5q (del(5q)), with or without additional cytogenetic abnormalities. In the EU, the Committee for Medicinal Products for Human Use (CHMP) adopted a positive Opinion on 25-Apr- 2013 for the use of Revlimid in the "treatment of transfusion-dependent anaemia due to low- or int-1-risk MDS associated with an isolated deletion 5q cytogenetic abnormality when other

therapeutic options are insufficient or inadequate," variation EMEA/H/C/717/II/056. The European Commission (EC) Decision was adopted on 13-Jun-2013 based on a condition to the EU marketing authorisation for the Marketing Authorisation Holder (MAH) to implement a non-interventional post-authorization safety study (PASS) (Revlimid, Annex IID to the EC Decision). As per the condition to the marketing authorisation, the MAH implemented this retrospective study to describe the post-marketing pattern of use of lenalidomide in MDS, both within and outside of the EU approved indication.

This lenalidomide retrospective study will also aim to gather additional safety information among MDS patients treated with lenalidomide outside the EU approved indication including the risk of progression to acute myeloid leukemia (AML) in a routine-care setting, depending on both sufficient patient numbers and availability of data within the selected data sources.

5.2 Background

The target population of lenalidomide in MDS with del(5q) has for a long time been erroneously identified with the so-called "del(5q) syndrome," first described by Van den Berghe in 1974 (Van den Berghe, 1974), and characterized by refractory macrocytic anemia, normal or elevated platelet counts associated with erythroid hypoplasia, dyserythropoiesis, modest excess of myeloblasts, hypolobulated megakaryocytes, and del(5q) in the presence of an otherwise normal karyotype. This syndrome is prevalent in females and has a low propensity to evolve into AML. In a case-series from the Düsseldorf MDS Registry, the cumulative incidence of AML among patients with the del(5q) syndrome was reported to be 8% (Germing, 2000). In contrast to patients with the "del(5q) syndrome," patients with IPSS low-/int-1–risk MDS with del(5q) also have well-defined additional risk factors such as additional cytogenetic abnormalities (Schanz, 2012), excess blasts (5% to 10%), severe anemia, and transfusion dependency (Malcovati, 2006; Malcovati, 2011). Depending on the presence of additional risk factors, the survival of these patients can be as low as 7 months.

Patients with del(5q) and complex karyotype have a very high risk of leukemic progression when compared to patients with isolated del(5q) or del(5q) + 1 additional cytogenetic abnormality. In a series of 541 patients with MDS and del(5q), patients with isolated del(5q) had a time to 25% probability of AML transformation of 65 months compared to the same rate of AML transformation of 14.9 months for patients with del(5q) + 1 additional cytogenetic abnormality and of only 4.7 months for patients with a complex karyotype (Mallo, 2011).

Data from the most complete series of untreated IPSS low- or int-1–risk MDS patients with del(5q) with survival data available was published by the Düsseldorf MDS group, who describe the natural history of the disease in a cohort of 381 patients included in the disease registry and treated only with supportive care (Germing, 2012). Patients with transfusion dependence had a 2-year cumulative risk of AML of 4.9% and a 5-year AML risk of 17.6%, higher than the figure previously reported by the same group for the "del(5q) syndrome."

In the seminal Phase 2, uncontrolled study (MDS-003) conducted in patients with low- or int-1–risk MDS del(5q) and transfusion dependence (median of 6 red blood cell [RBC] transfusions in the 8 weeks preceding study entry), patients were treated with lenalidomide at the

initial dose of 10 mg/day for 21 days (46 patients) or 28 days (102 patients) of each 28-day cycle (List, 2006). Seventy-six percent of 148 patients included in the study had a significant improvement of transfusion dependence and 67% of patients became transfusion independent. The median time to response to lenalidomide was rapid (4.6 weeks) and sustained; the median duration of transfusion independence was not achieved at the time of the primary publication, after a median follow-up of 104 weeks. The median increase in hemoglobin levels compared to baseline values was 5.4 g/dL. Thrombocytopenia and an increased transfusion need at study inclusion were predictive factors of no response.

Eighty-five patients were evaluable for the cytogenetic response (at least 20 cells in metaphase available both at study entry and after 24 weeks); of them 45% had a complete cytogenetic response, and 28% a partial cytogenetic response (decrease \geq 50% of the initial del(5q) clone size) (List, 2006).

A recent randomized, placebo-controlled, double-blind, Phase 3 study (MDS-004) compared 2 different initial regimens of lenalidomide (respectively 10 mg/day for 21/28 days and 5 mg/day continuously, in 28-day cycles) with placebo (Fenaux, 2011). After 16 weeks of double-blind treatment, patients who did not have at least a minor erythroid response (50% or greater reduction in transfusion numbers, compared to baseline) could interrupt the double-blind phase and continue the treatment with active drug in an open-label phase. The vast majority of patients initially allocated to placebo (except for 11 patients) crossed over to the active drug after 16 weeks. For all patients, the double-blind phase was interrupted after 52 weeks, and the study continued as open-label for up to 156 weeks (3 years). The primary endpoint was the transfusion independence maintained for at least 26 weeks (according to the International Working Group [IWG] criteria [Cheson, 2006]), and secondary endpoints were rate of erythroid response, cytogenetic response, overall survival (OS), rate of progression to AML, safety, and Health--related Quality of Life (HRQoL).

During the double-blind phase, 56.1% and 42.6% of patients allocated to lenalidomide 10 mg and 5 mg, respectively, compared with 5.9% of placebo patients met the primary endpoint of transfusion independence, maintained for at least 26 weeks (Fenaux, 2011). Responding patients had rapid (more than 80% of responding patients responded during Cycles 1 and 2) and long-lasting responses (the median duration of response was not yet achieved at the time of primary data publication). Similar to what had been observed in the previous Phase 2 trial (List, 2006), both lenalidomide treatment and platelets levels (platelets $\geq 150 \times 10^{9}$ /L) were independently associated with the achievement of transfusion independence (Fenaux, 2011). Cytogenetic response was 50% and 25% for patients treated with lenalidomide 10 mg and 5 mg, respectively, and the respective rate of complete cytogenetic response was 29.4% and 15.6%. Quality of life measured with the Functional Assessment of Cancer Therapy-Anemia (FACT-An) questionnaire at Week 12 was significantly improved compared with baseline values in patients who received lenalidomide compared to those who received placebo.

The study confirmed the tolerability profile of lenalidomide in MDS with del(5q) (Fenaux, 2011). The most frequently reported adverse events (AEs) (Grade 3 and 4 according to the National

Cancer Institute (NCI) Common Toxicity Criteria [CTC]) were deep vein thrombosis (6 cases), neutropenia, and thrombocytopenia and were more common during Cycles 1 and 2.

Overall, 52 patients (24.2%) had progression to AML; of these 4/11 (36.4%) were randomized to placebo, 17/56 (30.4%) initially randomized to placebo then crossed over to lenalidomide after 16 weeks, 16/67 (23.2%) were treated in the 5 mg arm, and 15/67 (21.7%) were treated in the 10 mg arm (Fenaux, 2011). The 2-year cumulative risk of AML progression in the combined lenalidomide arms was 16.8% (95% confidence interval [CI] = 9.8 to 23.7). Responding patients (transfusion independence maintained for 8 weeks or more) had a significantly lower cumulative risk of progression to AML. Median survival was 42.2 months, 35.5 months, and 44.4 months, respectively, for placebo, lenalidomide 5 mg, and lenalidomide 10 mg; transfusion independence for 8 or more weeks was associated with a 42% reduction in the risk of progression to AML and 47% reduction in the risk of death.

Lenalidomide and Risk of AML Progression in Patients with Transfusion-dependent IPSS Low- or Int-1–Risk MDS Del(5q)

A retrospective analysis was published (Kuendgen, 2012a) comparing the risk of progression to AML and OS in patients treated with lenalidomide (from Studies MDS-003 and MDS-004 combined (Fenaux, 2011; List, 2006) with that of similar patients from the Düsseldorf MDS Registry (previously described) who never received lenalidomide (Germing, 2012). The comparative study included only patients with transfusion-dependent anemia without concomitant thrombocytopenia (< $50,000/\mu$ L) or neutropenia (< $500/\mu$ L) to have comparable populations. Overall, the 2 cohorts included 295 lenalidomide-treated and 125 untreated patients.

To account for differences in person-time at risk in these 2 cohorts due to different starting points for follow-up (from diagnosis in the untreated cohort versus inclusion in the study for the treated cohort), *left truncation* was considered appropriate and adopted for all analyses in this study. The 2 cohorts were well balanced, except for a higher transfusion need for treated versus untreated patients (median of 6 versus 2 units of RBC/8 weeks); higher transfusion dependence is a well-known risk factor for progression to AML and reduced survival (Malcovati, 2006).

Based upon the competing-risk estimator with left truncation, the 2-year cumulative incidence of progression to AML was 6.9% and 12.1% for the cohort of treated versus untreated patients, respectively; the respective 5-year cumulative incidence was 22.8% and 19.9% (Kuendgen, 2012a). Two-year survival was 89.9% versus 74.4% in treated versus untreated patients. After adjustment for covariates, the risk of progression to AML was similar in the 2 cohorts (hazard ratio [HR] = 0.969), while the risk of death was significantly reduced in the lenalidomide-treated cohort (HR = 0.597, p = 0.012). The authors concluded that the treatment of patients with low- or int-1–risk MDS and del(5q) with lenalidomide did not increase the risk of progression to AML, but it possibly conferred a survival benefit in RBC transfusion-dependent patients with del(5q) low- or int-1–risk MDS.

A similar study previously compared the time to AML progression and survival in 95 low- or int-1–risk MDS del(5q) patients treated within the French ATU (Authorisation Temporaire d'Utilisation) cohort to 99 similar patients of the GFM (French MDS Group) who never received

lenalidomide (Adès, 2012). Two matched-pair cohorts were generated using a propensity score model to have comparable groups with similar baseline characteristics; again, to account for different timepoints of study entry in the 2 cohorts, this study also used the "left truncation" model. The 4-year estimated cumulative incidence of AML was 9% in patients treated with lenalidomide and 15.8% in controls who did not receive lenalidomide (p = 0.16).

Median survival after diagnosis was 150 months in the 71 patients treated with lenalidomide compared to 78 months in the 71 matched controls (HR = 0.47; 95% CI = 0.23 to 1.01; p = 0.06) (Adès, 2012). The 4-year survival after treatment onset was 67% in patients treated with lenalidomide and 73% in untreated patients (p = 0.15). Based on study results, the authors concluded there was no significant difference in AML progression and survival from diagnosis between the cohort treated with lenalidomide and the control cohort.

Thus, the data available so far suggest there is no increased risk of AML progression in patients with MDS del(5q) treated with lenalidomide compared to patients who never received the drug. However, due to the retrospective nature of those studies and the existing confounding factors, as well as the lack of a prospective, long-term, placebo-controlled, randomized clinical trial, it was not possible to understand whether the incidence of progression to AML reported in clinical trials was solely part of the natural history of the disease or if there also was a causal relationship between the administration of lenalidomide and progression to AML.

The MAH is, therefore, conducting a post-authorisation prospective disease registry in transfusion-dependent, IPSS low- or int-1-risk MDS with isolated del(5q) (Study MDS-010). The primary objective will be to ascertain if the true rate of AML progression in these patients treated with lenalidomide in the routine-care setting is similar to what has been previously reported in clinical trials and in existing disease registries and to detect any significant difference in progression to AML according to baseline risk factors compared to what was previously reported.

However, since the PRAC was also interested to know the pattern of use of lenalidomide in MDS both within and outside the EU approved indication in MDS, this additional specific retrospective drug-utilisation study has been designed. This study will collect retrospective information on the indication(s) of use of lenalidomide in MDS and will also enable a description of the safety of the drug outside EU the approved indication in MDS (ie, in patients with any type of MDS other than transfusion-dependent International Prognostic Scoring System [IPSS] low- or intermediate-1 [int-1]-risk MDS with isolated del(5q)).

With these two non-interventional MDS post-authorisation safety studies, the MAH is meeting its obligation as outlined in the condition to Marketing Authorisation in Annex IID of the Revlimid Product Information – "to gather safety data on the use of lenalidomide in MDS patients and monitor off-label use".

6 **RESEARCH QUESTION AND OBJECTIVES**

